6.4 Relationship to Study Product

Relatedness is an assessment made by a study clinician of whether or not the event is related to the study product. The relationship of all AEs to the study product will be assessed per the clinical judgment of the investigator based on the package insert and investigator's brochure, and as defined in Version 2.0, January 2010 (or most current version) of the DAIDS EAE Reporting Manual, which is available on the DAIDS Regulatory Support Center (RSC) website at <https://rsc.niaid.nih.gov/clinical-research->

sites/manual-expedited-reporting-adverse-events-daids. 'Not related' will be noted for AEs among participants who do not accept PrEP.

6.5 Grading Severity of Events

The Division of AIDS Table for Grading the Severity of Adult and Pediatric Adverse Events, Corrected Version 2.1, July 2017, will be used for determining and reporting the severity of adverse events. The DAIDS grading table is available on the DAIDS RSC website at <https://rsc.niaid.nih.gov/clinical-research-sites/daids-adverse-event-grading-tables>.

6.6 Serious Adverse Event (SAE)

The Serious Adverse Event (SAE) Reporting Category, as defined in Version 2.0 (or latest version) of the Manual for Expedited Reporting of Adverse Events to DAIDS, will be used for this study. Only SAEs deemed related to the study product must be reported in an expedited fashion to DAIDS.

All SAEs as defined by ICH guidelines regardless of relationship to the study agent(s) will be reported and are as follows:

- Results in death,
- Is life-threatening,
- Requires inpatient hospitalization or prolongation of existing hospitalization,
- Results in persistent or significant disability/incapacity, or
- Is a congenital anomaly/birth defect

Important medical events that may not be immediately life-threatening or result in death or hospitalization but may jeopardize the patient or may require intervention to prevent one of the outcomes listed in the definition above. Such determination may be made through medical or scientific judgment. Examples include the following: intensive treatment in an emergency room or at home for allergic bronchospasm; blood dyscrasias or convulsions that do not result in hospitalization; development of drug dependency or drug abuse; etc.

6.7 Discontinuation of Study Medication

Subjects may withdraw from the study at any time. Any participant who prematurely discontinues PrEP (for toxicity or pregnancy) should be followed for study duration. Subjects who become pregnant (non-pregnant cohort) or who acquire HIV infection will have study drug discontinued but will be followed to determine the pregnancy outcome.

6.8 Discontinuation of study drug with toxicity

Grade I or II toxicity will be managed in consultation with a clinician on the protocol. The clinician may add follow up testing and evaluations, as medically indicated. Study drug can be continued except as noted below.

Grade III toxicities will be communicated to the PSRT and managed under the direction of a study physician. Follow up testing and evaluations will be added, as medically indicated. The toxicity will be evaluated for subject safety. If the adverse event may put the subject at increased risk, or jeopardizes the study's intent, even if not related with study drug, the subject will discontinue study drug. The PSRT will decide whether study drug can be restarted. If the adverse event is deemed not to be a significant health risk, the PSRT may recommend continuing study drug with close monitoring.

Grade IV toxicities will be communicated to the PSRT and managed under the direction of a study physician. If a grade IV event is related to the study drug, the participant will permanently discontinue the study drug and will be followed as medically indicated. If the grade IV is not related to the study drug, the PSRT will recommend whether study drug can be continued with close monitoring, or permanently/temporarily discontinued.

Participants who discontinue drug permanently due to a study drug-related AE will be followed until AE resolves or stabilizes and then the subject will be discontinued from the study.

6.8.1 AE Grades 1 or 2

Grade I or II toxicity will be managed in consultation with a clinician on the protocol. The clinician may add follow up testing and evaluations, as medically indicated. Study drug can be continued except as noted below.

6.8.2 AE Grade 3

FTC/TDF may be continued as directed by the site investigator if a Grade 3 toxicity is considered to be unrelated to the study medication. Study medication will be temporarily withheld if Grade 3 toxicity is considered to be related to the study medication. After a Grade 3 toxicity returns to Grade 1, the participant can be reintroduced to medication after consultation with the site investigator, DAIDS Medical Officer, and other members of the PSRT. If a Grade 3 toxicity recurs and is considered to be related to study medication, FTC/TDF will be permanently discontinued.

6.8.3 Grade 4

For all Grade 4 laboratory-identified or clinical toxicities, FTC/TDF will be withheld unless it is determined to be not related. If a Grade 4 laboratory toxicity is not confirmed by repeat testing, it should be managed per algorithm for the new toxicity grade. Participants with Grade 4 AEs will be followed until the event resolves to baseline or stabilizes. Study drug may be restarted in the event of the resolution of a Grade 4 AE back to Grade 1, after consultation with the site investigator, DAIDS Medical Officer, and other members of the PSRT. If the toxicity recurs to Grade 3 or higher after FTC/TDF is restarted and is considered to be related to FTC/TDF, the study medication will be permanently discontinued.

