3.8 Replacement of Study Participants

Data from people who permanently discontinue study treatment will be used in analyses. Study participants who miss two consecutive scheduled dosing or miss any pharmacological samples or permanently discontinue DOT PrEP will be replaced so that approximately 60 evaluable participants complete the study. No more than 20% of the target population (n=60) will be replaced for maximum of 72 participants. Data from subjects who discontinue prematurely will be used in analyses. In the non-pregnant cohort, cisgender women who get pregnant will be replaced but continue to be followed up to the end of their scheduled protocol study follow up. Seroconversions (unlikely though possible) will not be replaced.

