At each scheduled pharmacological visit, antenatal records will be reviewed, and assessment of fetal heart tones will be conducted. After 8 weeks of DOT PrEP, pregnant cisgender women will be linked to continue PrEP at the clinic of their choice, including at the Thika site clinic itself, permitting seamless access to PrEP for and continuation for HIV prevention after the study. After 8 weeks of DOT PrEP, if a pregnant cisgender woman chooses not to continue with PrEP for protection against HIV, they may have two additional visits after their last PrEP dose – one visit at week 9 and a second visit within weeks 10 to 16. In the event of pregnancy loss during study follow up, study drug procedures and follow up will be terminated and women will be linked to appropriate clinical standard care including continued access for PrEP. After completing DOT phase of study, pregnant women will have observation visits until end of the study or up to the infant's first birthday (12 months) after delivery whichever occurs first to obtain pregnancy outcomes (i.e., term live birth, preterm birth, birth defects or pregnancy loss) and infant growth outcomes (i.e., weight, head circumference and height). Post DOT maternal/infant visit will 1 (i.e., birth visit), 6, and 12 months. Medical and medication history at birth will be reviewed and will consist of information recorded on medical records at birth as well as information obtained at the Birth Visit (Month 1 post-delivery).

The following should be source documented as part of medical and medications history at the Birth Visit: **Pregnancy/birth outcomes:** Term live birth, preterm birth, birth defects or pregnancy loss, Sex at birth Birth length, weight, and head circumference at birth (obtain from medical records; these measurements will also be performed by study staff at the infant Birth Visit), Apgar scores at one and five minutes (obtained from medical records)

Infant growth outcomes: obtained at 1, 6 and 12 months will include: Length, weight, and head circumference.

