want and might benefit from it), all pregnant cisgender women will be at high risk for HIV and will receive only daily PrEP dosing (7 doses per week). HIV risk and eligibility will be determined according to the Kenya guidelines for PrEP. Pregnant cisgender women will receive only daily PrEP dosing (7 doses per week). After 8 weeks of DOT PrEP, pregnant cisgender women will be linked to continue PrEP at the clinic of their choice, including at the Thika site clinic itself, permitting seamless access to PrEP and continuation after the study. For the initially non-pregnant cisgender women, if they become pregnant, study drug will be discontinued unless they have an indication for PrEP for which daily dosing will be provided. Cisgender women will be followed to obtain pregnancy outcomes until end of study.

Reducing social harm risks

In addition to protecting the privacy of participants, as described above, we will monitor for social harms. Social harms will be recorded on separate case report forms. Severe unexpected social harms will be considered unexpected problems and reported to the IRB according to local regulations. Social harms will be included on summary reports for the PSRT, as described in this protocol.

Reducing risks behavior disinhibition

We will use brief standardized questionnaires, which we have used for prior studies in cisgender women to explore partner number, sexual frequency, and condom use over time. Each visit will include risk-reduction counseling for all cisgender women and cisgender women will be provided with condoms. Importantly, only cisgender women at low risk of HIV will be enrolled in the non-pregnant cohort which has potential for assignment for non-daily dosing.

Reducing risks from other study procedures

The blood will be collected from an arm vein, and/or by finger stick, by trained staff at the study site according to standard medical procedures. Hematology will be monitored. The hair that is cut will be taken from underneath the top layer of hair to minimize the ability to see where the hair was cut from and to avoid sun-bleached hair.

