8.13 Study Discontinuation

The study also may be discontinued at any time by NIAID, other government or regulatory authorities (OHRP), or site IRBs/ECs.

Subjects may withdraw from the study at any time. Depending on the time point and circumstances of a subject's withdrawal they will be asked to complete/offer an "Early Discontinuation/Exit Visit" to confirm safety and health status as the time of withdrawal. The study investigators can remove a subject at any time if they deem that the study is no longer in the subject's best interest or the subject is not adhering to the protocol. Discontinuation of a subject by the PI/Co-I(s) could be a result of but is not limited to the following:

- Subjects who become incarcerated while on the study.
- who acquire other infectious diseases (i.e. not-HIV) while in the study will be reviewed by the PI/PSRT to confirm subject is still considered low-risk for HIV infection (See Exclusion criterion) This determination will be done by the PI/study physician.
- Subjects who are deemed to be non-compliant with the study medication(s) and/or procedures (e.g. 2 consecutive missed study visits or medication doses) may be discontinued from the study by the PI.
- Permanent study drug discontinuations for toxicity were described above. These participants will be followed until the completion of scheduled protocol study duration.
- Subjects who require an exclusionary medication during the study will be discussed among the PSRT. Participant's continued study involvement will be determined the PSRT and PI's.

The PSRT will be consulted if and when these circumstances arise.

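### Section 6.8 takes a woman off study once a drug-related adverse event settles, while 6.7 and 8.13 follow her to the scheduled end, so HIV tests and birth outcomes can be lost for women with toxicity

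*Combined protocol and SAP*

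**What the plan says.** **Stopping for toxicity.** Section 6.8 covers permanent stops for a drug-related adverse event. Such a participant "will be followed until AE resolves or stabilizes and then the subject will be discontinued from the study". Section 6.7 says: "Any participant who prematurely discontinues PrEP (for toxicity or pregnancy) should be followed for study duration". Section 8.13, on permanent stops for toxicity, says: "These participants will be followed until the completion of scheduled protocol study duration".

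**Incident pregnancy in the non-pregnant cohort.** Under 3.8 these women "will be replaced but continue to be followed up to the end of their scheduled protocol study follow up". Under 6.7 they "will have study drug discontinued but will be followed to determine the pregnancy outcome". Section 8.5 follows them for pregnancy outcomes until the end of the study. On drug, 6.7 makes no exception, while 8.5 says that "if they become pregnant, study drug will be discontinued unless they have an indication for PrEP for which daily dosing will be provided".

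**Pregnancy loss.** Section 5.4 says: "In the event of pregnancy loss during study follow up, study drug procedures and follow up will be terminated". Section 6.3 follows every reported adverse event until it resolves or stabilizes.

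**What follow-up collects.** Section 8.4 promises an HIV test at baseline and every 4 weeks. Section 5.2.2 and Table 5 place the on-study tests at weeks 4 and 8. Section 5.4 sets observation visits for pregnancy and infant outcomes, worded for women who have completed the observed-dosing phase. The interim review in 7.6 covers HIV infections and pregnancy outcomes.

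**The concern.** Every woman covered by the 6.8 exit clause is also covered by 6.7 and by 8.13, and those sections give her the opposite instruction. Unless her event lasts to the scheduled end, the site cannot meet all three.

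The women affected are not a random subset. They leave because of drug-related toxicity, so whatever is not collected afterwards is missing for a reason tied to safety. The pregnant cohort has at most 18 women, all enrolled because their HIV risk is elevated. Each woman who leaves before delivery removes 1/18 = 5.6% of that cohort's birth outcomes.

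**Working it through.** The plan states no figure to reproduce. The check sets the rules side by side and applies the visit schedule to them.

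1. **Overlap of the toxicity rules.** 6.8 applies to permanent stops for drug-related events. 8.13 applies to permanent stops for toxicity, and 6.7 to any early stop for toxicity. The 6.8 group lies inside both of the others. No text ranks the sections.

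2. **HIV tests missed under 6.8.** Tests fall at weeks 4 and 8 (5.2.2, Table 5). For an exit in week x, the tests missed are those scheduled after x:
   - weeks 1 to 3: both;
   - after the week 4 test, up to week 7: one;
   - after the week 8 test: none.

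3. **Delivery in the pregnant cohort.** Entry is at 13 to 26 weeks (2.5.2, 3.1). Assume birth at 37 to 40 weeks' gestation. Study week of birth = gestation at birth − gestation at entry:
   - earliest 37 − 26 = 11, latest 40 − 13 = 27;
   - 3.1 words the range as counted from conception; taking off 2 weeks gives 9 to 25.

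   Both ranges begin after the 8-week dosing period. One caveat applies: 3.1 sets the range at screening, and entry may be up to 30 days (30/7 = 4.3 weeks) later. The extreme early case is then 11 − 4.3 = 6.7 weeks, or 9 − 4.3 = 4.7. So an exit during dosing would normally, but not always, precede delivery.

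   Illustration, exit at study week 4: 40 − (26 + 4) = 10 and 40 − (13 + 4) = 23 weeks short of 40 weeks. Counted from conception this is 8 to 21.

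4. **Incident pregnancy.** Scheduled follow-up lasts up to week 16 (5.2). A woman who conceives at entry is 16 weeks past conception then, or about 18 weeks' gestation. Later conceptions are less advanced, so the 3.8 end point comes before any birth. Assuming conception in weeks 0 to 8 and birth 35 to 40 weeks later, birth falls at study weeks 0 + 35 = 35 to 8 + 40 = 48. That is 35 − 16 = 19 to 48 − 16 = 32 weeks after week 16.

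5. **Pregnancy loss.** 5.4 ends follow-up at the event, while 6.3 follows adverse events to resolution or stabilization. If the loss or a complication of it is an adverse event still unresolved, the two do not fit. Scheduled HIV tests after the loss also go.

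**The case against.** The strongest reply is that other text softens an early exit. Section 3.7 asks for every reasonable effort to complete final evaluations, 8.13 provides an exit visit, and 8.5 allows HIV testing as needed. The primary outcomes are drug concentrations, women who stop are replaced up to the cap in 3.8, and the 6.8 clause reaches only a small subset of at most 72. All of that stands and limits the size of the problem. It does not remove the contradiction, and an exit visit during dosing cannot record a birth that has not yet happened.

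A reader might go further than the documents allow in five ways:

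- **That the incident-pregnancy follow-up rules are opposite, so a site must breach one.** All three keep the woman in follow-up. A site that follows to outcome also satisfies 3.8 as a minimum, and none of the three skips an HIV test. The end points differ and need aligning. Only the drug instructions in 6.7 and 8.5 truly conflict.
- **That ending follow-up at pregnancy loss loses the pregnancy outcome.** The loss is the outcome, and 7.6 lists it. Whether 5.4 also conflicts with 6.7 depends on reading a stop for pregnancy to include a stop after its loss, which is doubtful.
- **That a woman stopping at week 2 is out by about week 4.** The 1 to 2 weeks in 8.5 is counselling text on self-limiting side effects. It says nothing about how long events leading to a permanent stop last.
- **That pregnancy outcomes would come only from women who tolerated the drug.** Women with unrelated events, temporary holds or successful restarts are outside the 6.8 clause.
- **That 6.7 already supplies the needed follow-up.** It mentions neither HIV tests nor adverse-event review, and Table 5 schedules neither after week 8.

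**Conclusion.** The contradiction between 6.8 and 6.7 with 8.13 is real and unresolved. A site that follows 6.8 as written can lose one or both on-study HIV tests. In the pregnant cohort it would normally lose the birth outcome as well, since the 5.4 visits are worded for women who complete dosing. The loss is selective, because it falls on women with drug-related toxicity. How many women this would be cannot be estimated from the documents; it is likely to be few. The delivery timings rest on the assumed lengths of gestation and on how 13 to 26 weeks is counted.

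Two further points stand. First, 6.7 and 8.5 disagree on study drug after an incident pregnancy, and the stated follow-up end points differ, with that in 3.8 falling before any birth. Second, and less important, 5.4 ends follow-up at a pregnancy loss, which sits badly with 6.3.

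**What to change.** Reconcile 3.8, 5.4, 6.3, 6.7, 6.8, 8.5 and 8.13 into one follow-up statement for each reason for stopping: drug-related toxicity, incident pregnancy and pregnancy loss. Each statement should separate stopping study drug from ending data collection, so that scheduled HIV tests and pregnancy outcomes are not lost merely because drug was stopped. It should give a single end point and say whether the 5.4 outcome visits apply to women who did not complete dosing.

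The drug instructions for incident pregnancy in 6.7 and 8.5 must also be reconciled. That is a clinical decision for the sponsor, and this review does not choose between them.

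The cost is protocol wording and a few extra contacts or visits. Birth-visit procedures already exist in 5.4. The downside is slightly longer follow-up for a few women.

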4.7 Toxicity Management

Safety related laboratory testing will be performed at study entry and at week 8 and or as indicated by clinician during follow up. If enrollment occurs more 30 days after screening, entry safety labs will be repeated (HIV rapid testing, Complete blood count, HBV surface antigen, serum creatinine, urine pregnancy tests. Toxicity will be managed in consultation with a clinician on the protocol. The clinician may discontinue the study drug at any time if he/she feels that continued use would be harmful to the participant. The PSRT should be consulted when possible. The PSRT will be consulted when considering further holding or recommencing study medication.

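### Sections 6.8 and 6.8.3 disagree on whether study drug may be restarted after a confirmed, drug-related Grade 4 event that resolves to Grade 1

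*Combined protocol and SAP*

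**What the plan says.** The opening text of section 6.8 sorts Grade 4 events by relationship to study drug. For related events: "If a grade IV event is related to the study drug, the participant will permanently discontinue the study drug". For unrelated events the decision passes to the PSRT: "If the grade IV is not related to the study drug, the PSRT will recommend whether study drug can be continued with close monitoring", or stopped permanently or temporarily. All Grade 4 events are reported to the PSRT.

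Section 6.8.3 covers Grade 4 again, in a different way. It starts with a hold: "For all Grade 4 laboratory-identified or clinical toxicities, FTC/TDF will be withheld unless it is determined to be not related". A laboratory result that repeat testing does not confirm is handled under its new grade. For events that remain Grade 4, the section continues: "Study drug may be restarted in the event of the resolution of a Grade 4 AE back to Grade 1", subject to consultation with the site investigator, the DAIDS Medical Officer and other PSRT members. Permanent discontinuation comes only at a later stage: "If the toxicity recurs to Grade 3 or higher after FTC/TDF is restarted and is considered to be related to FTC/TDF".

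Section 4.7 adds a general provision: "The PSRT will be consulted when considering further holding or recommencing study medication".

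**The concern.** Both sections address the same participant: a woman with a confirmed Grade 4 event, judged related to FTC/TDF, that has since come down to Grade 1. Under 6.8 her dosing has ended for good. Under 6.8.3 it may resume after consultation. A site that restarts her in line with 6.8.3 has departed from 6.8, and a monitor could cite 6.8 for a protocol violation.

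What is at stake is the clarity of a stopping rule at the highest toxicity grade that section 6.8 manages, in a trial that includes up to 18 pregnant women. The consultation step is the natural place to resolve a doubtful case. However, the two sections also differ on whether those consulted have a decision to make.

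**Working it through.** The documents give no figure to reproduce and no arithmetic applies. The check is a clause-by-clause comparison, followed by a search for anything that limits one rule or ranks the two.

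**Step 1. Outcome by type of event.**

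| Grade 4 event | 6.8 opening text | 6.8.3 | Conflict? |
|---|---|---|---|
| Determined to be not related | PSRT recommends continuing, or stopping temporarily or permanently | Exempt from the mandatory hold | No conflict on restart |
| Relationship not yet settled | Not addressed | Withheld; may restart at Grade 1 after consultation | Not necessarily |
| Related, confirmed, resolved to Grade 1 | Permanent discontinuation, no exception | Withheld; may restart at Grade 1 after consultation; permanent only on related recurrence at Grade 3 or higher | **Yes** |
| Laboratory value not confirmed on repeat | Not addressed | Managed under the new grade | No |

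**Step 2. Is the 6.8.3 restart limited to events that are not related?** The text does not say so, and its structure points the other way.
- The only events exempt from the hold are those determined to be not related. The events on hold, which are the ones a restart would concern, therefore include the related ones.
- The restart sentence carries no condition on relationship.
- The recurrence clause, "If the toxicity recurs to Grade 3 or higher after FTC/TDF is restarted and is considered to be related to FTC/TDF", makes discontinuation permanent after a restart. The sequence is hold, restart, then permanent stop on a related recurrence. Under 6.8 a related event ends dosing the first time.
- Section 6.8.2 uses the same sequence for Grade 3, and there the hold applies expressly to related events.

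**Step 3. Does any provision rank the two rules?** I looked at sections 3.8, 4.7, 4.9, 6.1, 6.7, 6.8.4, 8.4 and 8.13. None gives precedence to either section, and none limits the 6.8.3 restart. Section 4.7 requires consultation but does not say which Grade 4 rule the PSRT applies. Section 8.4 refers to stopping after serious drug side effects, but it names no grade and does not mention restart.

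**Step 4. Does consultation resolve the case?** In the opening text of 6.8, PSRT discretion over Grade 4 events is given only for the unrelated ones: "If the grade IV is not related to the study drug, the PSRT will recommend whether study drug can be continued with close monitoring". For a related event nothing is left to decide. Section 6.8.3 requires consultation before restart for events that include the related ones. The PSRT could be consulted in every case and still face two different statements of whether restart is open to it.

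**The case against.** The strongest reply is that the two sections do not give opposite orders. The restart in 6.8.3 is permissive. A site that withholds drug after a related Grade 4 event and never restarts it complies with both sections. That is correct. A reader might infer that both sections cannot be followed at once, and the documents do not support that. What remains is narrower: the permission in 6.8.3 extends to an act that 6.8 rules out.

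It can also be said that 6.8.3 has a wider reach than 6.8's rule for related events. It covers events whose relationship is unsettled, some of which may later be judged unrelated, and restart in those cases need not conflict with 6.8. This stands, and it limits the problem to events judged related.

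A third reply is that safeguards surround either reading. Drug stops under both sections, Grade 4 events go to the PSRT, and restart requires consultation that includes the DAIDS Medical Officer. Section 6.1 gives the PSRT a role in holds and permanent discontinuations. This answers any suggestion that a site could restart on its own authority. It does not remove the disagreement over whether restart is available.

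Two further inferences are tempting. One is that the choice of rule decides who is replaced under section 3.8. Section 3.8 also replaces anyone who misses two consecutive scheduled doses, and a hold lasting until a Grade 4 event falls to Grade 1 would usually cause that. Section 3.8 also keeps data from women who discontinue in the analyses. The other is that the conflict materially distorts the week 8 concentrations used for dose proportionality. The documents give neither a Grade 4 rate nor a length of hold, and drug is off under both rules until any restart, so no such effect can be shown.

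**Conclusion.** The point holds in a narrow form. For a confirmed, drug-related Grade 4 event that resolves to Grade 1, 6.8 prohibits restart and 6.8.3 permits it after consultation. Nothing in the protocol says which governs. The protocol is wrong as written here, because a restart made in line with one section breaches the other.

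Its reach is every event of that kind, in either cohort and any arm, among up to 72 women. The number of such events cannot be estimated from the documents. The conclusion rests on the ordinary reading of the two sections and on the absence of any precedence statement. It depends on no numerical assumption. Its importance lies in participant safety and protocol compliance. It does not rest on sample size or on the primary estimates.

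**What to change.** Reconcile the opening text of 6.8 with 6.8.3 so that both state the same rule on whether restart is possible after a related Grade 4 event. The revised text should also make clear whether the PSRT has discretion in that case, and how events of unsettled relationship are treated until they are classified. The choice of rule is for the sponsor's clinicians, and this review takes no position on it.

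Section 3.8 needs no change for this purpose. The cost is a wording amendment with the usual approvals. Sample size, data collection and analysis are unaffected.
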